8.3.1. Clinical Safety Laboratory Assessments

- See Appendix 2 (Section 10.2) for the list of clinical laboratory tests to be performed and the SoA for the timing and frequency.
- The investigator must review the laboratory report, document this review, and record any clinically relevant changes occurring during the study in the AE section of the eCRF. The laboratory reports must be filed with the source documents.
- All laboratory tests with values considered clinically significant during participation in the study or within 14 days after the last dose of study drug should be repeated until the values return to normal or baseline or are no longer considered clinically significant by the Investigator or Sponsor's Medical Monitor (or designee). If such values do not return to normal/baseline within a period of time judged reasonable by the investigator, the etiology should be identified, and the Sponsor notified.
- Laboratory values which are abnormal AND lead to either the requirement for an intervention, the requirement for additional medications, or are felt to otherwise be medically important should be recorded as adverse events in the eCRF.
- Hematology or serum chemistry parameters will be graded according to the FDA toxicity grading scale (Section 10.3.1.1.2) and will be adjusted according to local laboratory reference ranges. Participants have the ability to rescreen once should screening values fall outside of the allowed eligibility criteria, per the discretion of the Investigator.

8.4. Adverse Events and Serious Adverse Events

The definitions of any AE (solicited and unsolicited), SAE and AESIs/NOCIs can be found in Appendix 3 (Section 10.3).

The investigator and any qualified designees are responsible for detecting, documenting, and recording events that meet the definition of any AE (solicited and unsolicited), or SAE. Investigators remain responsible for following up AEs, SAEs and other reportable safety events for outcome.

8.4.1. Time Period and Frequency for Collecting AE, SAE and Other Reportable Safety Event Information

All AEs (solicited and unsolicited), SAEs and other reportable safety events that occur after the consent form is signed but before study administration must be reported by the investigator if the event cause the participant to be excluded from the study or is the result of a protocol-specified intervention, including but not limited to washout or discontinuation of usual therapy, diet, or a procedure.

Table 5 below summarizes the different reporting timelines for AEs (unsolicited and solicited), SAEs, SUSAR and pregnancy.

Medical occurrences that begin before the start of study drug but after obtaining informed consent will be recorded on the Medical History/Current Medical Conditions section of the eCRF not the AE section.

All SAEs will be recorded and reported to the Sponsor or designee immediately and under no circumstance should this exceed 24 hours, as indicated in Appendix 3 (Table 17). The investigator will submit any updated SAE data to the Sponsor within 24 hours of it being available.

Table 5	Adverse	Event	Reporting	Timelines	to the	Sponsor

Type of Event	AE (unsolicited)	AE (solicited)	SAE / AESI / NOCI	Pregnancy
Reporting period	From first dose until 4 weeks after last dose of study drug	1 week after each study drug administration	From first dose until end of Follow-Up Period/ EOS	From first dose until end of Follow-Up Period/ EOS
Reporting Timelines to the Sponsor	Entered into the clinical database on an ongoing basis	Entered into the clinical database on an ongoing basis	Within 24 hours	Within 24 hours
Reporting Method	AE eCRF	Solicited Symptom Diary	AE eCRF or SAER Form	Pregnancy form

AE, Adverse event; SAE, Serious adverse event; SUSAR, serious unexpected suspected adverse reaction.

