^e If participants are not eligible to receive their 2nd dose, they immediately enter the follow-up period.

^f AEs will only be collected for 4 weeks following each study drug administration.

^g An aliquot of serum collected at baseline will be stored for testing (e.g. Platelet Factor 4 [PF4] antibody ELISA) should an AESI related to blood clots be reported anytime during the study period.

Follow-Up Period							
		COHORT 1	COF	IORT 2	COHORT 3		
Study Day	Months 3, 4, Month 7 5, 6 (Wk 28)/ EOS		Months 4, 5, 6, 7	Month 8 (Wk 32)/EOS	Months 5, 6, 7, 8	Month 9 (Wk 36)/ EOS	
Telephone Visit	Х		Х		Х		
Visit Window (days)	±7	±7	±7	±7	±7	±7	
Query for SAEs, AESIs and NOCIs	Х	Х	Х	Х	Х	Х	
Sample Collection Immunoger	nicity Assessme	nts					
Serum		Х		Х		Х	
Whole blood (Flow Based)							
Whole blood (PBMC) ^a		Х		Х		Х	
Nasal Swab (Sam Device)		Х		Х		Х	
Saliva		Х		Х		Х	

AE, adverse event; AESI, Adverse event of special interest; EOS, End of Study; ET, Early Termination; HCV, Hepatitis C Virus; HIV, Human Immunodeficiency Virus; NP, Nasopharyngeal; NOCI, New Onset of Chronic Illness; PBMC, peripheral blood mononuclear cells; SAE, serious adverse event. ^a Optional.

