8.2. Safety Assessments

The safety of the VXA-G1.1-NN will be evaluated through the reporting of solicited symptoms of reactogenicity for 1 week following each study drug dose, unsolicited AEs for 4 weeks following each study drug dose, SAEs (including AESIs and NOCIs) for 6 months following the last study drug dose. The occurrence of these events should be reported to the Sponsor in an expedited manner, similarly to SAEs as described in Table 9. AESIs are listed in Appendix 5 (Section 10.5).

Planned time points for all safety assessments are provided in the SoA (Table 2).

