- Unsolicited AEs are any AEs reported spontaneously by the participant, observed by the study personnel during study visits or those identified during review of medical records or source documents. Unsolicited AEs (all AEs not collected in the Solicited Symptom Diary during the first week following each study drug administration) will be monitored and collected from the time of each dose through 4 weeks post each dose.
- Solicited AEs are predefined systemic signs and symptoms of reactogenicity for which the participant is specifically questioned, and which are noted by the participant in their Solicited Symptom Diary, including:
 - fever (any temperature 100°F or higher)
 - headache
 - myalgia (muscle pain)
 - abdominal pain
 - anorexia (defined and not eating)
 - nausea
 - vomiting
 - diarrhea
 - malaise/fatigue

Participants will utilize a Solicited Symptom Diary issued on the day of each study drug administration to record solicited AE daily for the 1 week following each dose.

Table 8Events Meeting Definition of AE

Events Meeting the AE Definition

- Any abnormal laboratory test results (hematology, clinical chemistry, or urinalysis) or other safety assessments (e.g., vital signs measurements) that worsen from baseline and are considered clinically significant in the medical and scientific judgment of the investigator.
- Exacerbation of a chronic or intermittent pre-existing condition including either an increase in frequency and/or intensity of the condition.
- New conditions detected or diagnosed after study drug administration even though it may have been present before the start of the study.
- Signs, symptoms, or the clinical sequelae of a suspected intervention- intervention interaction.
- Signs, symptoms, or the clinical sequelae of a suspected overdose of either study intervention or a concomitant medication. Overdose per se will not be reported as an AE/SAE unless it is an intentional overdose taken with possible suicidal/self-harming intent. Such overdoses should be reported regardless of sequelae.

Events **NOT** Meeting the AE Definition

- Events that occurred from consent to pretreatment
- Medical or surgical procedure (e.g., endoscopy, appendectomy): the condition that leads to the procedure is the AE.
- Situations in which an untoward medical occurrence did not occur (social and/or convenience admission to a hospital).

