4.2 Secondary endpoints

- Frequencies, durations, and severities of solicited symptoms of reactogenicity (local, systemic) for 1 week following each dose of study drug by treatment group
- Frequencies, durations, and severities of unsolicited AEs, SAEs, AESIs and NOCIs through each active study period (4 weeks post each vaccination) by treatment group
- Number and percentages of subjects with ≥2-, 3-, 4-fold increase over baseline titer of Norovirus G1.1 HBGA BT50 results by treatment group and visit
- Geometric Least Square Mean (LSM) of post-dose Norovirus G1.1 HBGA BT50 titer by treatment group and visit adjusted for baseline titer level
- Least Square Geometric Mean Ratio (LS-GMR) of post-dose titer Norovirus G1.1 HBGA BT50 between treatment groups by visit adjusted for baseline titer level

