7.0 Statistical Considerations and Analysis

7.1 Derived Variables

The below table provides the list of derived variables for demographic and baseline characteristics, various duration derivations, baseline derivation and other important derivations applicable for this study.

Table 4: Derived Variables

Variables	Formula			
Demographic and Baseline Characteristics				
Age at informed consent (in years)	Integer ((date of informed consent – date of birth + 1) / 365.25)			
Body Mass Index	Weight (kg) / height (m)²			
Derivation of Durations				
Study day at any visit	Date of interest – date of first dose of vaccine. One day is added if the difference is ≥ 0 .			
Duration of any events	End date of event – start date of event + 1			
Baseline Derivations				
Laboratory baseline	The baseline value is defined as the last observation prior to or on the date of the first dose of study drug.			
Change from baseline	Post baseline value – baseline			
Percent change from baseline	[(Post baseline value – baseline) / baseline] * 100			
Change from previous visit	Current value – previous value			
Percent change from previous visit	[(Current value – previous value) / previous value] * 100			
Other Derivations				
Geometric mean/geometric, mean titer/geometric mean concentration	Individual values will be transformed via the natural log, mean values along with 95% CIs will be calculated, which will be transformed back to the original scale via exponentiation.			
Geometric mean fold rise	The mean values and 95% CIs of the log ratio of post dose assay values relative to baseline will be calculated, then transformed back to the original scale via exponentiation.			
Geometric least square mean	Least square means and 95% CIs for each treatment group will be calculated from ANCOVA with immunogenicity assay result on log scale at post dose visit as a dependent variable, treatment group as a factor and baseline immunogenicity assay result on log scale as a covariate, which will be then transformed to the original scale via exponentiation.			
Least square geometric mean ratio	Least square mean differences and 95% CIs among treatment groups will be estimated from the abovementioned ANCOVA model, which will be then transformed to the original scale via exponentiation.			

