8.7 Safety analysis

This section describes the safety analyses that will be conducted during the active and follow-up periods (i.e., the safety analyses on all data collected during the active and follow-up periods and all data collected in subjects who dropped-out during the active and follow-up periods).

All definitions relative to safety endpoints are detailed in Section 4.4.

Safety analyses will be conducted on the safety population and will be performed for all safety variables specified below.

All safety data will be summarized by cohort and study visit as well as by overall study population.

The safety analyses of changes from baseline to a specific time point in safety variables (e.g., vital signs) will only include subjects from the safety population who have data available at both the baseline and the time point under considerations unless otherwise specified.

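### Protocol Table 5 and the schedule footnote give different collection periods for unsolicited AEs in Cohorts 2 and 3, and the SAP's AE methods do not apply the 4-week window its own endpoint names

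*Protocol*

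**What the plan says.** **Continuous period.** Protocol Section 8.4.1, Table 5, gives the reporting period for unsolicited AEs as "From first dose until 4 weeks after last dose of study drug". In Protocol Section 9.2.1, the secondary-endpoint row is also headed as running from Day 1 to the end of the Active Period. The text of that row nevertheless repeats the limit of four weeks after each vaccination.

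**Per-dose period.** Footnote f of the Schedule of Activities (Protocol 1.2, repeated in SAP Table 2) says "AEs will only be collected for 4 weeks following each study drug administration". Protocol Section 8.2 refers to "unsolicited AEs for 4 weeks following each study drug dose". Appendix 3, Table 7, says that unsolicited AEs "will be monitored and collected from the time of each dose through 4 weeks post each dose". SAP 4.2 defines the endpoint "through each active study period (4 weeks post each vaccination) by treatment group".

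**SAP methods.** SAP 7.1 derives study day as "Date of interest – date of first dose of vaccine", with a day added on or after dosing; nothing is anchored to the second dose. SAP 8.7 describes "the safety analyses on all data collected during the active and follow-up periods" and adds: "All safety data will be summarized by cohort and study visit as well as by overall study population". SAP 8.7.1 summarises AEs by cohort, severity and relatedness. It counts a participant once per term within a treatment period that it does not define. It gives no onset window and no split by dose.

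**The concern.** The secondary objective is safety and tolerability at different boost intervals, and the by-cohort AE table is where a reader will set the three intervals side by side. The days on which the two rules differ run from Day 29 to the boost. Their number grows with the interval, which is the variable under study.

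If events from those days are recorded and tabulated, an identical vaccine would show more participants with AEs at longer intervals because they were observed for longer. The error runs one way. Such events can be recorded even at a site that does not work from Table 5: the boost visit includes an assessment for acute illness or new medical conditions, safety laboratory tests and a medication review, and clinically relevant laboratory changes go into the AE section of the eCRF (Protocol 8.3.1).

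Summarising by study visit does not resolve this, because the SAP does not say to which visit an AE starting between visits belongs.

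**Working it through.** **Inputs.** Second dose on Day 29, 57 or 85 (SAP 3.3); end of the Active Period at Week 8, 12 or 16, that is Day 57, 85 or 113 (Protocol 4 and 1.2); 10 participants per cohort; a second dose may be up to 7 days late (SAP 8.5). The documents give no background AE rate.

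**1. The plan's own figure.** Boost day + 28: 29 + 28 = 57, 57 + 28 = 85, 85 + 28 = 113. This matches the schedule.

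**2. Length of collection, on-time boost.**

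| Rule | Cohort 1 | Cohort 2 | Cohort 3 |
|---|---|---|---|
| Table 5 (end day − 1) | 56 | 84 | 112 |
| Footnote f (28 + 28) | 56 | 56 | 56 |
| Difference, days | 0 | 28 | 56 |

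The ratio under Table 5 is 1 : 1.5 : 2. If every boost were 7 days late, the differences would be 7, 35 and 63 days, so the rules agree in Cohort 1 only when the boost is on time. For a participant who receives only the first dose they coincide in every cohort.

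**3. Illustrative effect on the percentage with at least one AE.** Assume a constant rate r of unsolicited AEs per person per 28 days, the same in every cohort, and no vaccine effect. Then P(at least one AE) = 1 − exp(−r·k), where k is the number of 28-day blocks observed. Full capture gives k = 2, 3, 4; half capture of between-period events gives k = 2, 2.5, 3; equal windows give k = 2 throughout.

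| r (assumed) | Full capture, C1/C2/C3 | C3 − C1, points |
|---|---|---|
| 0.1 | 18.1 / 25.9 / 33.0% | 14.8 |
| 0.3 | 45.1 / 59.3 / 69.9% | 24.8 |
| 0.5 | 63.2 / 77.7 / 86.5% | 23.3 |

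At r = 0.3 with half capture the percentages are 45.1 / 52.8 / 59.3%, a gap of 14.2 points between Cohorts 3 and 1. With equal windows the gap is 0.

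**4. Chance that the table points the wrong way.** Let X1 and X3 be independent binomial counts with n = 10. P(X3 > X1) is the sum over i of P(X1 = i)·P(X3 > i). At r = 0.3:

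- full capture (45.1% against 69.9%): 0.82
- half capture (45.1% against 59.3%): 0.66
- equal windows (45.1% in both): 0.41, with the same chance the other way and the remainder ties

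At r = 0.1 with full capture the probability is 0.70.

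**The case against.** The strongest reply is that the documents largely settle which rule governs. The per-dose window appears in the endpoint tables, footnote f, Section 8.2, Appendix 3 and SAP 4.2; the continuous period appears in one Table 5 cell and one heading. Protocol Section 8 makes adherence to the Schedule of Activities mandatory. Its AE query row follows the per-dose rule: after Day 29, Cohort 2 is next queried at Day 64 and Cohort 3 at Day 92, both after the boost. This stands. It makes the continuous reading less likely and any capture of between-period events probably partial.

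A reader might infer that the SAP has no window at all. It has one, in SAP 4.2, and SAP 3.1 defines Study Periods 1 and 2. What is missing is the step that applies them to the tables. The table templates are in a separate document, so a split by period may exist there, but the SAP does not require it.

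A reader might also infer that the excess could not be detected. With 30 participants and every AE listed, it could be found by comparing onset and dosing dates. The summary table alone would not show it.

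It is also fair that no between-cohort test of AEs is planned, that allocation is not randomised, and that the summary by relatedness might place many background events under not related. These points limit the consequence; they do not equalise the windows.

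Finally, a reader might infer that AESIs go unmonitored between Day 29 and the boost. They are reportable continuously from first dose to end of study and are queried at later visits and calls, so the point does not extend to them.

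**Conclusion.** The conflict between the two collection rules is real, and the SAP methods leave it unresolved. The nominal difference is 0, 28 and 56 days in Cohorts 1, 2 and 3. A bias follows only if events with onset between Day 29 and the boost enter the database. The documents do not support saying that this will happen, or that capture would be complete.

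If it does happen, the direction is fixed: longer intervals look less well tolerated. On assumed rates of 0.1 to 0.5 per 28 days, full capture adds about 15 to 25 percentage points to Cohort 3 relative to Cohort 1, or 1.5 to 2.5 of 10 participants. Half capture at 0.3 adds about 14 points. These figures rest on a constant, equal background rate, no vaccine effect and on-time boosts. This is worth correcting because the correction is cheap, but it is a modest point about a descriptive table.

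**What to change.** 1. Align the Table 5 cell with footnote f. Enrolment is complete (Protocol Appendix 7), so for this trial that mainly puts the intended rule on record; it matters more for any protocol built on this one.
2. In SAP 7.1, derive for each AE the days from the most recent dose. Assign it to Study Period 1 (onset within 28 days after dose 1 and before dose 2), between periods, or Study Period 2 (onset within 28 days after dose 2).
3. In SAP 8.7.1, define the treatment period as onset within 28 days after each dose, and tabulate unsolicited AEs by cohort and Study Period. Participants who receive both doses then contribute 28 + 28 days whichever rule the site followed.
4. List between-period AEs separately, with a note on whether the site collected them systematically. Flag AEs with start dates imputed under SAP 7.3, which may fall in the wrong period.
5. Keep the 6-month SAE, AESI and NOCI summary as planned.

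If the Active Period tables are already final, report items 2 to 4 in the follow-up addendum (SAP 8.8) as a described deviation from the SAP.

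The cost is one derived variable from AE start dates and dosing dates already recorded, one split of an existing table and one listing. The drawback is that between-period AEs leave the main table, and their listing may be incomplete if the site followed footnote f. The note in item 4 is there to say so.

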8.4.2. Method of Detecting AEs and SAEs

Appendix 3 (Section 10.3) provides the method of recording (Table 10), evaluating severity (Table 11), and assessing causality (Table 16) of AEs and SAEs and the procedures for completing and transmitting SAE reports (Table 17).

Care will be taken not to introduce bias when detecting AEs or SAEs. Open-ended and nonleading questioning of participants is the preferred method to inquire for AE occurrences.

8.4.3. Follow-Up of AEs and SAEs

The investigator is obligated to perform or arrange for the conduct of supplemental measurements and evaluations as medically indicated to elucidate the nature and causality of the AE or SAE as fully as possible. This may include laboratory tests or investigations, histopathological examinations, or consultation with other health care professionals.

The investigator will submit updated SAE data to Sponsor within 24 hours of receipt of the information. AEs and pregnancy will be followed by the investigator as specified in Appendix 4.

8.4.4. Regulatory Reporting Requirements for SAEs

- Prompt notification by the investigator to the Sponsor of a SAE is essential so that legal obligations and ethical responsibilities towards the safety of participants and the safety of the study drug under clinical investigation are met.
- The Sponsor has a legal responsibility to notify both the local regulatory authority and other regulatory agencies about the safety of the study drug under clinical investigation. The Sponsor will comply with country-specific regulatory requirements relating to safety reporting to the regulatory authority, Institutional Review Boards (IRB) and investigators.
- Investigator safety reports must be prepared for SUSAR according to local regulatory requirements and Sponsor policy and forwarded to investigators as necessary.
- An investigator who receives an investigator safety report describing a SAE or other specific safety information (e.g., summary or listing of SAEs) from the Sponsor will review and then file it along with the IB and will notify the IRB, if appropriate, according to local requirements.

8.4.5. Death Events

Events resulting in death will be an SAE regardless of association to study drug. Death is an outcome and should not be reported as an event term. The event that leads to the death should be reported as the SAE term.

8.4.6. Pregnancy

- Details of all pregnancies in female partners of male participants will be collected as outlined in Appendix 4 (Section 10.4).
- If a pregnancy is reported, the investigator should inform the Sponsor within 24 hours of learning of the pregnancy and should follow the procedures outlined in Appendix 4 (Section 10.4.3).

9.2. Statistical Analyses

The statistical analysis plan (SAP) will be developed and finalized before database lock for any of the planned analyses. It will describe the participant populations to be included in the analyses and the procedures for accounting for missing, unused, and spurious data. This section provides a summary of the planned statistical analyses of the primary, secondary, and tertiary/exploratory endpoints.

